This will be a randomized, assessor and participant-blinded study. Adult patients (aged 20 years or older) scheduled for surgical treatment for hip fracture with American Society of Anesthesiologists (ASA) physical status I-III will be assessed for eligibility to participate the study. The exclusion criteria includes: allergy to local anesthetics, pregnancy, inability to understand and use the numerical rating scale (NRS 0-10, 0: no pain, 10: worst pain imaginable) after instruction, chronic use of opioids, coagulopathy, neuropathy or severe diabetic mellitus. If the patients give his /her informed consents, his/her baseline demographic data (gender, age, height, and body weight) and types of hip fracture will be recorded. Participants will be randomly allocated into either FIC block or PENG block by using the website RESEARCH RANDOMIZER (<https://www.randomizer.org>). One of the two anesthesiologists experienced in performed the FIC and PENG blocks will perform the nerve blocks. Only the anesthesiologist performing the nerve block and his assistant will be aware of which nerve block the participant received immediately

before performing nerve block by opening a sealed envelope. The assessors, in-charge anesthesiologists and nurse anesthetists, operation room personnel, surgeons and study participants will be all blinded to the randomization. The participants are unlikely to know which nerve block they receive because the needle insertion sites and needle trajectories of these two nerve blocks are quite close to each other.

On arrival of the operating theater, all participants will be sent to the nerve block area, where continuous electrocardiogram (ECG), pulse oximetry, and non-invasive intermittent blood pressure monitoring will be applied and an intravenous line will be established. Before any intervention, pain at rest and during the fractured lower limb being passively internal rotated in extension to neutral position from its usual externally rotated deformity by assessors will be assessed using NRS. If the participant cannot tolerate passive internal rotation of his/her fractured limb due to pain, impossibility to perform the test will be recorded as well as the worst NRS score during these attempts. The same assessment will be performed every 10 mins for until 30 mins after completion of the nerve block. Then the patient will be sent to the operation room, where spinal anesthesia will be performed for the surgery.

Procedures of the nerve blocks

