The primary outcome of this study is the pain measurement at rest and during the fractured limb being passively internally rotated 30 mins after nerve block. The secondary outcomes includes the pain measurement during positioning for spinal anesthesia (from supine to lateral decubitus with flexion of the healthy hip), pain measurement at 6, 12, and 24 hours after operation, the time spending for performing spinal anesthesia (defined as starting of positioning maneuver to removal of spinal needle), quality of position for spinal anesthesia (characterized as unsatisfied, satisfied, good, and excellent by the anesthesiologists performing the spinal anesthesia), the time interval between the end of operation and pain first perceived by the patient, the time interval between the end of operation and the first request for rescue analgesics, total consumption of rescue analgesics within 24 hours after the operation, the time interval between the end of operation and the first time the patient can ambulate with assistance after operation, the time spending for nerve block (defined as from contact of skin by the ultrasound transducer to removal of the needle), and satisfaction of the patient regarding preoperative analgesia from nerve block (very good, good, adequate, poor, very poor) inquired on the 1st postoperative day.

Statistics

Based on a previous study, the standard deviation of pain score after FIC block was 2.4¹⁰. Assuming the minimal clinically important difference in NRS score is 1.5, 44 patients in each group are required to achieve a power of 80% and a level of significance of 5% (two sided). One hundred eligible patients (50 patients in each group) will be enrolled in the study after informed consents are obtained. The data of normal distribution will be analyzed with independent *t*-test, otherwise Mann-Whitney U test will be used for analyses. Categorical data will be analyzed using χ^2 test or Fisher's exact test. $P < 0.05$ will be considered statistically significant.

There is no conflict of interest.

Reference

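### Postoperative pain at 6, 12 and 24 h has no planned overall estimate and no arm-by-time test; one repeated-measures model would supply both at little cost (optional, secondary outcome)

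*Combined protocol and SAP*

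**What the plan says.** The Outcome measurements section of the combined protocol and SAP lists "pain measurement at 6, 12, and 24 hours after operation" as one of ten secondary outcomes. Each patient therefore gives three postoperative readings on the "numerical rating scale (NRS 0-10, 0: no pain, 10: worst pain imaginable") defined under Methods.

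The Statistics section covers all numeric outcomes in one sentence. It opens "The data of normal distribution will be analyzed with independent" *t*-test and ends "otherwise Mann-Whitney U test will be used for analyses". Chi-square or Fisher's exact test is kept for categorical data, and P < 0.05 "will be considered statistically significant".

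The section defines no mean or area under the curve over the three times, no repeated-measures model, no arm-by-time test and no handling of a missed reading. It does not say in words that each time will be tested separately. But the tests it names take one value per patient and no summary value is defined, so separate comparisons are what it implies.

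**The concern.** Three readings from one patient are correlated, and three two-sample tests make no use of that. There are two consequences.

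- **No overall comparison.** Nothing planned answers whether pain over the first 24 postoperative hours differed between the blocks. An average over the three times would usually be estimated more precisely than the difference at any one of them.
- **No test of change.** If the 6 h comparison reaches P < 0.05 and the 24 h comparison does not, that does not show that the difference shrank. Only a direct arm-by-time contrast can show it, and none is planned.

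In addition, the normality rule allows a t-test at one time and a rank test at another. Those two results are not on a common scale and cannot be set side by side as a time course.

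This differs from the question of how many tests share the 5% level. Adjusting alpha would supply neither an overall estimate nor a test of change.

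**Working it through.** **Inputs from the Statistics section.** SD 2.4 (given for pain after FIC block); difference 1.5 ("Assuming the minimal clinically important difference in NRS score is 1.5"); two-sided 5%; 80% power; 44 per group required; "One hundred eligible patients (50 patients in each group) will be enrolled in the study".

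**Assumptions not in the documents.** SD 2.4 also holds at 6, 12 and 24 h. The within-patient correlation rho is equal for every pair of times and lies between 0.3 and 0.9. The true difference is the same at all three times. Data are complete. A 1.0-point difference is shown beside the plan's 1.5 as a smaller alternative.

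**Step 1: the plan's own figure.** The normal approximation gives 2 × [2.4 × (1.960 + 0.842) / 1.5]² = 40.2, so 41 per group. The exact t-test calculation gives 41.2, so 42. Dividing 41.2 by the Mann-Whitney relative efficiency 3/π = 0.955 gives 43.1, so 44. The stated 44 is reproduced in that last form. The documents do not say how it was obtained.

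**Step 2: precision.** At one time the standard error of the difference is 2.4 × sqrt(2/50) = 0.48. The mean of three equally correlated readings has variance SD² × (1 + 2 rho)/3, so its standard error is 0.48 × sqrt((1 + 2 rho)/3). At rho 0.5 this is 0.48 × sqrt(2/3) = 0.48 × 0.816 = 0.39.

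**Step 3: power, from the noncentral t with 50 per arm.** At one time it is 54% for 1.0 point and 87% for 1.5 points, whatever rho is.

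| rho | SE of average | Relative efficiency | Power of average, 1.0 point | Power of average, 1.5 points |
|---|---|---|---|---|
| 0.3 | 0.35 | 1.88 | 81% | 99% |
| 0.5 | 0.39 | 1.50 | 71% | 97% |
| 0.7 | 0.43 | 1.25 | 64% | 93% |
| 0.9 | 0.46 | 1.07 | 57% | 89% |

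**Step 4: false signs of change.** Trials were simulated with a constant difference and three separate t-tests each. The table gives the share of trials in which 6 h is significant and 24 h is not, and the share with any mixture of significant and non-significant times.

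| rho | 6 h yes, 24 h no: 1.0 point | 6 h yes, 24 h no: 1.5 points | Any mixture: 1.0 point | Any mixture: 1.5 points |
|---|---|---|---|---|
| 0.3 | 20% | 10% | 60% | 29% |
| 0.5 | 17% | 8% | 50% | 25% |
| 0.7 | 13% | 6% | 38% | 19% |
| 0.9 | 7% | 4% | 21% | 11% |

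**Step 5: a fading effect.** Suppose the differences are 1.5, 0.75 and 0 at 6, 12 and 24 h. Their mean is (1.5 + 0.75 + 0)/3 = 0.75. At rho 0.5 the average has 47% power, against 87% for the 6 h contrast alone. An average cannot therefore replace the per-time estimates.

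**The case against.** The case for leaving the plan alone is substantial.

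- **The per-time tests are valid.** This stands. With complete data and no baseline covariate, a model with unstructured covariance returns the same difference at each time as the separate comparisons. A reader might infer that the plan loses precision at every time point. It does not: the gain belongs to the average over the three times, which the plan never names as a target.
- **The documents do not say that duration will be judged from these P values.** This also stands. The plan lists outcomes closer to duration: time to first pain, time to first rescue request and 24 h rescue use. The title and the primary outcome concern pain before surgery, and no hypothesis about change over time is stated. The gap is only that, should anyone wish to make such a statement from the 6, 12 and 24 h scores, the plan gives no valid means.
- **The misleading pattern is a minority result.** Also correct. A reader might take the 50% mixed-pattern figure (1.0 point, rho 0.5) as the chance that a constant effect seems to wear off. That figure includes trials significant only at 12 h or only at 24 h. The pattern that looks like wearing off occurs in about 17% there, and in about 8% at the plan's own 1.5 points.
- **The gain rests on assumptions.** The correlation, the postoperative SD and a constant effect after a single preoperative injection are all assumed. At rho 0.9 the gain almost disappears (57% against 54% at 1.0 point), and under a fading effect the average does worse than the 6 h contrast.
- **A Gaussian model would drop the plan's provision for non-normal data.** True of the model alone, so a rank-based check has to go with it.

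A loss of patients with a missed reading could be argued too, but the documents give no loss rate and it cannot be sized.

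What remains is the absence of any overall estimate and of any arm-by-time test.

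**Conclusion.** The point holds as a modest one. The plan implies three valid but unconnected comparisons of the same patients. It forgoes a more precise overall comparison and gives no valid basis for saying that the difference between blocks changes over time.

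At the plan's 1.5 points, the average would raise power from 87% to between 89 and 99%. At 1.0 point it would raise it from 54% to between 57 and 81%. A constant effect would look like one that wears off in roughly 4 to 10% of trials at 1.5 points and 7 to 20% at 1.0 point. All of this rests on SD 2.4 at the postoperative times, a constant difference and rho between 0.3 and 0.9. The documents support none of these three directly.

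The primary outcome at 30 minutes and the sample size are unaffected. This is an optional improvement to one secondary outcome, not an error that threatens the trial's main conclusion.

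**What to change.** Add one or two sentences to the Statistics section:

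- Analyse the 6, 12 and 24 h NRS in one repeated-measures model with arm, time and arm × time, and unstructured covariance within patient.
- Report the average difference over the three times and the difference at each time, all with 95% CIs.
- Base any statement that the difference changes over time on the arm × time term. A non-significant term should not be read as proof that the difference is constant.
- Keep a rank-based check for non-normal data, for example a Mann-Whitney test on each patient's mean score.

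The cost is slightly more analysis work, with no extra patients, visits or data. There are two downsides. The average blurs a fading effect (47% against 87% power in the example above), which is why the per-time estimates stay in the report. The model is Gaussian on a bounded 0-10 score, which is why the rank-based check is kept.

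### Two ordered rating scales have no named test, and the plan's categorical-data rule would ignore the order of their grades

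*Combined protocol and SAP*

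**What the plan says.** The Outcome measurements section of the combined protocol and SAP includes two ratings recorded as ordered words, both secondary outcomes:

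- Positioning: "quality of position for spinal anesthesia (characterized as unsatisfied, satisfied, good, and excellent by the anesthesiologists performing the spinal anesthesia"), four grades.
- Satisfaction: "satisfaction of the patient regarding preoperative analgesia from nerve block (very good, good, adequate, poor, very poor) inquired on the 1st postoperative day", five grades.

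The Statistics section has two general rules. Normally distributed data get an independent t-test, "otherwise Mann-Whitney U test will be used for analyses". The second rule reads "Categorical data will be analyzed using χ^2 test or Fisher's exact test". Neither rule mentions ordinal data or either scale, and no other section assigns them a test. The document's title says that it contains the SAP, and it points to no further analysis document.

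**The concern.** Two rules are available and they lead to different tests. The Mann-Whitney rule is worded as the fallback when data are not normal, a check one makes on numeric measurements. Grades recorded as words are usually tabulated as counts and called categorical. The ordinary reading therefore sends both ratings to chi-square or Fisher.

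Those tests treat the grades as unordered labels. They ask whether the two grade distributions differ in any way, not whether one block is rated higher. Two things follow. A consistent shift towards better grades is harder to detect. And a significant result can arise when neither block is rated better, yet be reported as a difference in quality or satisfaction. Because the plan does not settle the choice, the analyst could also make it after seeing the data.

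**Working it through.** **Plan's own figures.** The plan gives none for these scales. Its 44 per group concerns the pain score (SD 2.4, difference 1.5, 80% power, two-sided 5%). A t-test calculation gives 41.17, so 42. Dividing by the Mann-Whitney efficiency 3/π gives 41.17 / 0.955 = 43.11, so 44. The stated figure is therefore reproducible, and it does not bear on this point.

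**Inputs.** From the plan: 50 per group, two-sided 5%, four and five grades. Assumed: all grade counts, distributions and odds ratios below.

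**Formulas.** With equal groups and counts a and b in each grade, chi-square = Σ (a − b)² / (a + b), with (grades − 1) degrees of freedom. Mann-Whitney uses z = (W − 2525) / √V. Here W is the first group's sum of midranks, 2525 = 50 × 101 / 2, and V = (50 × 50 / 12) × [101 − Σ(t³ − t) / (100 × 99)], with t the total in each grade.

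**Example 1, a shift: 10/17/15/8 vs 5/12/17/16 (worst to best).**
- Chi-square: 25/15 + 25/29 + 4/32 + 64/24 = 1.667 + 0.862 + 0.125 + 2.667 = 5.32 on 3 df, p = 0.15. Fisher by full enumeration: p = 0.15.
- Mann-Whitney: the grade totals are 15, 29, 32, 24 and the midranks 8, 30, 60.5, 88.5. W = 80 + 510 + 907.5 + 708 = 2205.5. Σ(t³ − t) = 74,256, so V = 208.33 × (101 − 7.50) = 19,479 and √V = 139.6. z = −319.5 / 139.6 = −2.29, p = 0.022.

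**The same table with its columns shuffled: 8/17/10/15 vs 16/12/5/17.** The four chi-square terms are the same in another order, so the statistic is still 5.32 and p still 0.15. For Mann-Whitney the midranks become 12.5, 39, 61, 84.5. W = 100 + 663 + 610 + 1267.5 = 2640.5, z = 115.5 / 139.6 = 0.83, p = 0.41. Only Mann-Whitney responds to the order.

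**Example 2, no shift: 4/21/21/4 vs 13/12/12/13.**
- Chi-square: 81/17 + 81/33 + 81/33 + 81/17 = 14.44 on 3 df, p = 0.002. Fisher also gives p = 0.002.
- Mann-Whitney: both groups are symmetric about the middle of the scale, so W = 2525, z = 0, p = 1.00.

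**Example 3, five grades: 5/10/20/10/5 vs 2/6/18/14/10.**
- Chi-square: 9/7 + 16/16 + 4/38 + 16/24 + 25/15 = 4.72 on 4 df, p = 0.32. Fisher: p = 0.34.
- Mann-Whitney: p = 0.03.

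**Power.** Simulation with 50 per group and a proportional-odds shift, 20,000 runs per cell, using four assumed distributions for each scale (even, peaked in the middle, and skewed each way).

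| Odds ratio | Power lost by chi-square against Mann-Whitney (percentage points) |
|---|---|
| 1.5 | 7–9 |
| 2 to 3 | 14–18 (four grades), 19–24 (five grades) |
| 4 | 6–13 |
| 5 | 2–7 |

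At odds ratio 2.5, four even grades give 54.0% for chi-square and 71.4% for Mann-Whitney. Five grades with probabilities .1, .2, .4, .2, .1 give 47.3% and 70.4%. At odds ratio 2, power is low either way: 26–33% against 43–49%. Exact Fisher (2,000 runs per cell, three distributions per scale) loses 13–19 points on four grades and 15–25 on five at odds ratios 2 to 3.

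With no difference, rejection rates were 4.0–5.7% for chi-square, 4.5–5.7% for Fisher and 3.9–5.3% for Mann-Whitney. Any of the three, fixed in advance, is valid at about 5%.

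**The case against.** The strongest reply is that the plan contains no error, only an unlabelled choice. The Mann-Whitney clause is not expressly limited to measured quantities, and ranked grades fit it. If that was the intention, the power loss disappears. This stands, and it is why the consequence is conditional. The ambiguity still remains, because nothing in the text rules out the categorical reading, which is the more usual one.

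Tests are also assigned by data type for every outcome, so the absence of a named test is not peculiar to these scales. That is fair. What sets them apart is that either rule could be taken to cover them.

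Chi-square and Fisher keep their error rate, and they detect patterns that Mann-Whitney misses. In Example 2 the lowest grade rises from 4/50 to 13/50, which a reader might want to know, and Mann-Whitney returns p = 1.00. In two assumed patterns with a difference in spread only, chi-square has 77% and 93% power against about 6% for Mann-Whitney. The plan states no hypothesis for either scale, so the directional question is a judgement. It is the natural one for a scale running from worst to best in a comparison of two blocks, but the trade-off is real.

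Finally, the sizes rest on assumed distributions. The proportional-odds model favours Mann-Whitney, and odds ratios 2 to 3 are where the gap is widest. All of that stands: the figures illustrate what is at stake and do not forecast this trial.

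**Conclusion.** The concern holds as a minor point. The plan does not say which of its two rules covers the positioning and satisfaction ratings, and the tests in its categorical rule ignore the order of the grades. If that rule is applied and the true difference is a consistent shift with odds ratio 2 to 3, chi-square gives up roughly 14 to 24 points of power, depending on the number of grades. Outside that range the loss is smaller. The size depends on the categorical reading, on the proportional-odds form and on the assumed grade distributions. The two scales are secondary outcomes. The primary outcome, the sample size and the error rate of a pre-chosen test are unaffected.

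**What to change.** Add one sentence to the Statistics section: positioning quality and patient satisfaction are ordered ratings and will be compared between groups with the Mann-Whitney test. Keep chi-square or Fisher for unordered data such as gender and fracture type, which the Methods section says will be recorded. Optionally, report a common odds ratio with a 95% confidence interval from a proportional-odds model, which gives an effect size at the price of one further assumption.

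The change needs no new data, and the test is already in the plan. Its cost is near-blindness to a difference in spread without a shift. Tabulating the full grade counts by group would keep such a pattern visible to the reader.

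### Three postoperative time-to-event outcomes are to be compared by t-test or Mann-Whitney, with no observation limit and no rule for patients who do not have the event

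*Combined protocol and SAP*

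**What the plan says.** Under Outcome measurements, the Combined protocol and SAP lists three secondary outcomes timed from the end of the operation:

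- first pain: "the time interval between the end of operation and pain first perceived by the patient"
- first rescue: "the time interval between the end of operation and the first request for rescue analgesics"
- assisted walking: "the time interval between the end of operation and the first time the patient can ambulate with assistance after operation"

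None has a stated end of observation. Nothing says what is recorded for a patient who feels no pain, asks for no rescue, or is not seen to walk.

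Two neighbouring outcomes carry a 24 h mark: "total consumption of rescue analgesics within 24 hours after the operation" and "pain measurement at 6, 12, and 24 hours after operation". Neither mark is attached to the three times.

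Under Statistics, normally distributed data "will be analyzed with independent *t*-test, otherwise Mann-Whitney U test will be used for analyses". Categorical data go to the chi-square or Fisher's exact test. No survival method, censoring rule or missing-data rule appears anywhere in the document.

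**The concern.** Both planned tests need one value, or at least one rank, per patient. A patient without the event has neither until a rule supplies it. Applied as written, the tests can use only patients who had the event.

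Having the event is itself a result of treatment. A block that spares more patients from pain loses its best results from the comparison, so the two groups compared are no longer those that were randomised.

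At stake are the size of the estimated difference, the power to detect it and, in some patterns, its direction. Without a prespecified rule, the choice would be made after the data are seen, and a reader could not tell which comparison was reported.

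**Working it through.** **Inputs.** From the document: 50 patients per arm, two-sided 5%, last pain score and rescue window at 24 h. Everything else is assumed, because the document gives no event rates, discharge times or deaths. The plan gives no figure for these outcomes to reproduce; its only calculation, 44 per group, concerns the pain score.

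**1. Proportional hazards, 24 h limit.** Times are exponential, with hazard = −ln(event-free share at 24 h)/24. The hazard ratio is the ratio of the two logs; for 2% v 8%, ln(0.08)/ln(0.02) = 2.526/3.912 = 0.65. Power from 4,000 simulated trials per row (Monte Carlo standard error at most 0.8 points):

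| Event-free at 24 h | Hazard ratio | Mann-Whitney, event-free dropped | Mann-Whitney, tied at 24 h | Log-rank |
|---|---|---|---|---|
| 1% v 3% | 0.76 | 17% | 21% | 27% |
| 2% v 8% | 0.65 | 31% | 47% | 57% |
| 5% v 15% | 0.63 | 24% | 50% | 59% |
| 20% v 40% | 0.57 | 13% | 61% | 66% |

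The cost of the missing rule is the gap between the dropped and tied columns: 4, 16, 26 and 48 points. At 2% v 8% it comes from about 1 v 4 patients of 50 (50 × 0.02 = 1; 50 × 0.08 = 4). The gap between tied and log-rank reflects the choice of test under exponential times, not the missing rule.

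**2. Size of the estimate.** With 20% event-free in one arm and hazard ratio 0.5, the other arm has 0.20^0.5 = 45% event-free. Dropping these patients gives a mean difference of 1.5 h and 14% power. Setting them to 24 h gives 4.6 h and 78%.

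**3. No true difference.** With equal shares of 5%, 20% or 40%, rejection is between 4.4% and 5.7% under dropping (t-test or Mann-Whitney), tying and log-rank.

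**4. Direction.** Let 20% of arm A and 40% of arm B be event-free, with event times exponential truncated at 24 h and scales of 15 h (A) and 8 h (B).

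- Mean among patients with the event, s − 24q/(1 − q) with q = exp(−24/s): 8.93 h (A), 6.74 h (B).
- 24 h restricted mean: A, 0.8 × 8.93 + 0.2 × 24 = 11.9 h; B, 0.6 × 6.74 + 0.4 × 24 = 13.6 h. B is better.
- Median among patients with the event, −s·ln(1 − 0.5(1 − q)): 7.6 h (A), 5.2 h (B). A looks better.

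The dropped analysis is significant in favour of A in 28% of simulated trials. With ties at 24 h this happens in 0.3%.

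**5. Assisted walking.** Assume exponential times with medians of 2 v 3 days (3,000 trials per setting, standard error at most 0.9 points).

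- Last observation uniform between days 3 and 7, independent of walking. The share not seen to walk is (2^(−3/m) − 2^(−7/m)) × m/(4 ln 2), which is 19% for m = 2 and 33% for m = 3. Power: 11% dropped, 35% with last-observation time entered as if it were the event (Mann-Whitney), 41% log-rank.
- Fixed 7-day limit. The share is 2^(−7/m), which is 9% v 20%. Power: 15% dropped, 40% tied, 46% log-rank.

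**The case against.** The strongest reply is that the large losses arise only if event-free patients are dropped, and the plan does not say they will be. A reader might infer that it does, because the tests run literally leave no other course. The documents support less: they are silent. For first pain and first rescue, 24 h is a natural limit, and ranking ties there keeps the planned Mann-Whitney test. For those two outcomes the gap could be closed by a sentence. That stands, but an inferred limit still does not say whether such a patient is dropped, set to 24 h or tied.

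A reader might also infer that Mann-Whitney is the wrong test and log-rank the right one. That does not follow. The log-rank advantage comes from assuming exponential times: with no event-free patients and a hazard ratio of 0.67 it is already 52% v 41%. With lognormal times shifted by 0.5 SD on the log scale the order reverses, 68% for Mann-Whitney v 63% for log-rank. With 5% v 13% event-free in that setting, Mann-Whitney has 66% tied and 50% dropped, so the cost of dropping remains.

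It is also fair that all event rates are assumed, that the reversal needs unequal shares, earlier events in the arm with more event-free patients, and dropping, and that the walking runs with varying follow-up take the last observation as independent of walking. These points limit the size of the concern; they do not remove it.

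**Conclusion.** The point holds as a gap in the analysis of three secondary outcomes that should be closed. It is widest for assisted walking, which has no 24 h anchor and where follow-up may differ between patients.

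If event-free patients are left out, the comparison conditions on having the event. Under the assumed shares of 2% v 8% and 20% v 40%, Mann-Whitney power falls from 47% to 31% and from 61% to 13%. Under non-proportional timing the sign can change. If very few patients are event-free the loss is smaller: 4 points at 1% v 3%.

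A reader might take this as a threat to the trial's main result. It is not: the primary outcome is measured 30 minutes after the block, the sample size rests on the pain score, and type I error stays near 5% in the settings run.

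**What to change.** **First pain and first rescue.** State a common observation limit; 24 h matches the existing assessments. Then prespecify one of two analyses: Mann-Whitney with event-free patients ranked as tied at the limit, or Kaplan-Meier with the log-rank test, censoring at the limit or at last contact if earlier. Neither is uniformly more powerful. Tied ranking suits patients all followed to the limit; if some are lost earlier, the second option handles them. Drop the t-test for these outcomes: values piled up at a limit are not normal, and their mean is a truncated one.

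**Assisted walking.** Set one fixed observation limit, and record walking status and last-contact time for every patient. Use Kaplan-Meier with log-rank. If deaths before walking occur, use cumulative incidence with Gray's test instead, because ordinary Kaplan-Meier and log-rank do not treat death as a competing event.

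**All three.** Report the number of patients without the event in each arm.

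**Cost.** A few lines of SAP wording, standard software and a little extra data recording. There is no change to sample size, primary analysis or patient care.

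### Time to first assisted ambulation lacks its baseline: patients unable to walk before the fracture may be enrolled and cannot be identified from the planned data

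*Combined protocol and SAP*

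**What the plan says.** Under Outcome measurements, the combined protocol and SAP includes among the secondary outcomes "the time interval between the end of operation and the first time the patient can ambulate with assistance after operation". It states no end of observation for this outcome.

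Under Methods, entry is open to "Adult patients (aged 20 years or older) scheduled for surgical treatment for hip fracture with American Society of Anesthesiologists (ASA) physical status I-III". The exclusions are local anaesthetic allergy, pregnancy, inability to use the pain scale, and "chronic use of opioids, coagulopathy, neuropathy or severe diabetic mellitus". Neuropathy comes nearest to mobility, but it does not remove people who were bed- or chair-bound for other reasons.

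At consent, "his/her baseline demographic data (gender, age, height, and body weight) and types of hip fracture will be recorded". Apart from the pain scores taken before the block, no other baseline measure is listed. On allocation the text says "Participants will be randomly allocated into either FIC block or PENG block", with no stratification.

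Under Statistics, measured outcomes go to the independent t-test if normally distributed; "otherwise Mann-Whitney U test will be used for analyses". No censoring, covariate, or rule for a patient who never walks is given.

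**The concern.** Whether and when a patient walks after hip surgery depends first on whether that patient walked before the fracture. The pain outcome has its own baseline, because pain is scored before the block. The ambulation outcome has none.

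A prior non-walker and a prior walker who recovers slowly look the same in the planned data: neither has an ambulation time. The analyst then has two simple choices, and neither is clean:

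- Ranking everyone without a time last lets prior disability into the comparison.
- Dropping everyone without a time selects on something that happens after randomisation, and discards the slow recoverers whom the outcome is meant to capture.

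A censoring rule alone does not solve this, because it cannot show which patients never had a possible event. Pre-fracture status is fixed before allocation, so restricting to it or stratifying by it keeps the randomised comparison intact. It has to be recorded for that to be possible.

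**Working it through.** **The plan's own figure.** The only sample size stated is 44 per group, for pain: "Assuming the minimal clinically important difference in NRS score is 1.5", with SD 2.4, two-sided 5% and 80% power.

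- Normal approximation: 2 × (2.4 × (1.960 + 0.842) / 1.5)² = 40.2, so 41 per group.
- t-test: 41.2, so 42 per group.
- Dividing 42 by the Mann-Whitney relative efficiency of 0.955 gives 43.98, so 44.

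The figure reproduces, but it says nothing about ambulation. The documents give no SD, effect or event share for that outcome.

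**Chance imbalance in prior non-walkers.** The arm size of 50 comes from Statistics. The share p of prior non-walkers is an assumption. Each arm's count is Binomial(50, p), so the expected count is 50p and the SD of the between-arm difference is √(2 × 50 × p × (1 − p)). At p = 10% this is √9 = 3.0. The probabilities are exact, from the joint distribution of the two counts.

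| Assumed share | Expected per arm | SD of difference | P(difference ≥ 3, either way) | P(difference ≥ 5, either way) |
|---|---|---|---|---|
| 2% | 1.0 | 1.4 | 0.07 | 0.003 |
| 5% | 2.5 | 2.2 | 0.24 | 0.04 |
| 10% | 5.0 | 3.0 | 0.40 | 0.13 |
| 15% | 7.5 | 3.6 | 0.48 | 0.21 |
| 20% | 10.0 | 4.0 | 0.53 | 0.26 |

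**Dilution if non-walkers are ranked last.** Mann-Whitney tests were simulated with 50 per arm and 4,000 runs per setting. The assumed effect among walkers is 0.625 SD. This is the pain ratio 1.5/2.4, borrowed only to have a scale. All walkers are taken to reach the event.

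| Assumed share | Power, non-walkers ranked last | Power, prior walkers only | Type I error, ranked last |
|---|---|---|---|
| 0% | 85% | 85% | 4.8% |
| 5% | 78% | 84% | 4.7% |
| 10% | 67% | 82% | 5.0% |
| 20% | 49% | 77% | 5.0% |

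Ranking non-walkers last costs power and leaves type I error at about 5%. Restricting to prior walkers recovers most of the loss despite the smaller sample. The simulation does not cover the other route, in which every patient without a time is dropped, because no prior walker in it fails to walk.

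**The case against.** A reader might infer that prior non-walkers will be counted as results of the block, or that the comparison is biased toward one arm. The documents support neither reading.

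- **Handling is unstated.** A patient who never walks has no value to enter in a t-test or Mann-Whitney test. That patient might be dropped, left missing or given a late value. A shift in the tail arises only if such patients are ranked last.
- **Allocation is random.** Prior non-walkers are balanced in expectation, and the significance test already allows for chance imbalance. The same could be said of any unmeasured prognostic factor at this sample size.
- **The share is assumed.** Limiting entry to ASA I-III, requiring use of the pain scale, and excluding neuropathy and severe diabetes may all lower it. At 2% the problem is small. The power figures borrow an effect from pain and are only illustrative.
- **Little rests on this outcome.** The aim and the sample size concern pain, and ambulation is one of about ten secondary outcomes.

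All four points stand, and they limit the concern to dilution and an imbalance that cannot be checked. They do not remove it. Unlike most unmeasured prognostic factors, this one makes the event impossible for some patients, and the planned data cannot show who they are. Hospital records might supply the information later, but the plan makes no provision for that.

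**Conclusion.** The point holds as a gap in one secondary outcome. Prior non-walkers may be enrolled, cannot be identified from the listed baseline data, and have no handling rule. The consequence is lost precision and a result that is hard to interpret. The validity of the test is not in question, there is no systematic bias toward either block, and the primary pain outcome and its sample size are untouched.

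The size rests on an assumed share, since the documents give none. At 5% to 10%, about 2.5 to 5 patients per arm have no possible event, and a difference of 3 or more between arms has a probability of 0.24 to 0.40. If they are ranked last and the effect among walkers is 0.625 SD, power falls from about 85% to between 78% and 67%. This is a low-priority improvement, worth making because it is cheap.

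**What to change.** 1. Add pre-fracture walking status (independent / with aid / not walking) to the baseline data taken at consent.
2. State in Statistics that time to first assisted ambulation is analysed in participants who walked before the fracture, stratified by independent versus with aid. Name a method that can use a stratum, such as a stratified log-rank test or a stratified rank test. The plain t-test and Mann-Whitney test cannot.
3. Define the end of observation for this outcome. Keep prior walkers who have not walked by then in the analysis, censored at that time under the log-rank test or ranked last under the rank test.
4. Report the number of prior non-walkers in each arm.

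The cost is one question at an existing contact and a few sentences in the SAP. A few patients leave this one secondary comparison, and the default test is replaced for it. Eligibility, treatment and sample size do not change.
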